6.2 DATA SHARING PLANS

6.2.1 Human Data Sharing Plan

What data will be shared?

I will share human data generated in this research for future research as follows:

- Coded, linked data in an NIH-funded or approved public repository.
- Coded, linked data in BTRIS (automatic for activities in the Clinical Center)
- Coded, linked or identified data with approved outside collaborators under appropriate agreements.

How and where will the data be shared?

Data will be shared through:

- BTRIS (automatic for activities in the Clinical Center)
- Approved outside collaborators under appropriate individual agreements.
- Publication and/or public presentations.

When will the data be shared?

- Before publication.
- At the time of publication or shortly thereafter.

6.2.2 Genomic Data Sharing

Unlinked genomic data will be deposited in public genomic databases such as dbGaP in compliance with the NIH Genomic Data Sharing Policy.

6.3 RESPONSE CRITERIA

6.3.1 General

The primary efficacy endpoint for this study is progression free survival (PFS) from patient registration. However, objective response status should be measured and recorded.

6.3.2 Definitions

Evaluable for maximum tolerated dose: All subjects enrolled in the Phase I dose escalation cohorts from the time of their first treatment with Zotiraciclib (TG02) +TMZ to the end of cycle 1. Patients who develop a DLT during cycle 1 and thus do not complete treatment for the cycle should be considered evaluable for MTD.

Evaluable for toxicity: All eligible patients who complete at least one cycle of protocol therapy or who have a DLT after the protocol therapy is started are evaluable for toxicity from the time of their first treatment.

*If the patients miss doses of Zotiraciclib (TG02) or TMZ in the first cycle of treatment due to reasons that are unrelated to toxicity, it will be the PI's decision about whether they are evaluable for toxicity in the dose finding stage.

Evaluable for objective response: Only those patients who have measurable disease present at baseline, have received at least one cycle of therapy at MTD and have had their disease re-evaluated will be considered evaluable for response. These patients will have their response classified according to the definitions stated below. (Note: Patients who exhibit objective disease progression prior to the end of cycle 1 will also be considered evaluable.)

Phase I patients removed from study treatment within 28 days for reasons other than toxicity may be replaced.

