1 INTRODUCTION

1.1 STUDY OBJECTIVES

1.1.1 Primary Objectives

1.1.1.1 Phase I

To determine the maximum tolerated dose (MTD) of Zotiraciclib (TG02) plus TMZ using both the dd and mn TMZ schedules in adult patients with recurrent anaplastic astrocytoma or glioblastoma/gliosarcoma.

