1.1.2 Secondary Objectives

1.1.2.1 To select the treatment regimen with better PFS4 between Zotiraciclib (TG02) plus dd TMZ or mn TMZ at each of the MTDs following cohort expansion.

1.1.2.2 To determine the objective response rate, PFS at 6 months (PFS6) and overall survival (OS) in the treatment arms.

1.1.2.3 To longitudinally evaluate patient reported outcome measures using self-reported symptom severity and interference with daily activities using the MDASI-BT

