In phase I, for each arm, the maximum sample size of 24 patients will be used for dose finding. As there are 4 doses, on average at least 6 patients will be treated at the MTD. After the MTD is selected, cohort expansion will be conducted at the MTD until the total number of patients treated at the MTD reaches 18 patients (including the patients who have been treated in the dose-finding part). Thus, no more than 12 additional patients will be enrolled during the cohort expansion phase. Therefore, the maximum number of patients for phase I, including dose finding and cohort expansion, is 24+12=36 patients per treatment arm, and 72 in total for two treatment arms.

During the interim analysis of the Phase I study, we identified TG02 of 250 mg as the MTD in both Arm 1 and Arm 2. Cohort expansion was conducted independently at each of the MTD into treatment arms, and the PSF4 was found to be 38% in Arm 1 and 25% in Arm 2. Therefore, based on the preplanned analysis, the DD TMZ dosing schedule is considered a “winner” to be used in Phase II study. However, a better PFS was found in patients who received TG02 at dose level 0, compared to those received TG02 at dose level 1, which is MTD, in Arm 1, the winner arm, suggesting the lower dose with the scheduled TMZ may be sufficient if not more beneficial for patients with recurrent high grade astrocytoma. However, we cannot make the conclusion based on the small sample number in Arm 1 at dose level 0. Therefore, we would like to continue enrolling to the maximum, allow the additional 12 patients enrolled to be treated with TG02 at dose level 0 combined with dd TMZ.

We do not plan to change the study design. The primary endpoint is still toxicity. The objective is to add a small cohort expansion to better characterize the dose-toxicity relationship and obtain some preliminary efficacy readout to determine RP2D. If PFS4 month difference between MTD and (MTD-1) is less than 5%, select the lower dose, I.e., MTD-1, as the RP2D; otherwise select the MTD as RP2D.

There should not be safety concerns because additional patients will be treated with TG02 at a dose that is lower than the MTD that was identified previously.

The purpose for enrolling more patients is to further define a dosage not only safe but optimal for the patients before we move to Phase II study. Only AE and PFS4 will be recorded in these subjects.

10.2 PHASE II COMPONENT:

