A randomized phase II trial will be used to compare the combination of Zotiraciclib (TG02) plus TMZ (selected from phase I) with TMZ alone in patients with recurrent grade III or IV malignant glioma. The TMZ alone arm will use the same dosing schedule as it is in the combination arm. The primary endpoint is progression free survival. We will enroll at least 10 patients and at most 40 patients for each arm at a rate of 4 patients per month. Patients will be equally randomized into two arms. Patients' KPS, MGMT promoter methylation status of the tumors and the presence of measurable disease at study entry will be used as stratification factors. We will follow all patients for at least 12 months, and monitor futility and toxicity as described below. We will use the methods described by Thall et al., to monitor progression-free survival (PFS), and we will stop enrolling patients early if, based on the available data, we have reason to believe that the median PFS of the Zotiraciclib (TG02) plus TMZ arm is less than that of the TMZ arm.^[50] Formally, we will stop enrolling patients early if

$$\Pr(\text{median PFS}_{\text{TG02+TMZ}} \geq \text{median PFS}_{\text{TMZ}} \mid \text{data from the trial}) < 0.78,$$

The futility monitoring will be conducted after enrolling 20, 40 and 60 patients (for two arms combined). Below are the operating characteristics of the above futility monitoring rule, assuming that the median PFS of the TMZ alone arm is 3 months.

Table 15 Operating Characteristics of the Futility Monitoring rule

	Median PFS for Zotiraciclib (TG02) +TMZ (months)				
	1	2	3	4	5
Early stop probability	0.999	0.812	0.374	0.170	0.097
Average sample size	23.7	42.1	62.6	70.9	74.7

Similar Bayesian methods will also be used to monitor the rate of DLT. We will monitor the two arms independently. Specifically, we will stop enrolling patients if the $\Pr(\text{DLT} > 35\% \mid \text{data}) > 0.9$. That is, we will stop enrolling patients if the data indicate that there is more than 90% chance that the true DLT rate is higher than 35%. This decision rule gives the following stopping rule, assuming a Beta (0.1, 0.4) prior distribution for DLT rate,

Stop enrolling pts if $[\# \text{ of pts with DLT}] / [\# \text{ of pts evaluated}] \geq 4/5, 6/10, 10/20, \text{ and } 15/30$.

Below are the operating characteristics of the toxicity monitoring rule.

Table 16: Operating Characteristics of the Toxicity Monitoring Rule

	True toxicity rate				
	0.2	0.3	0.4	0.5	0.6

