Early stop probability	0.014	0.096	0.345	0.716	0.939
Average sample size	39.6	37.3	31.0	21.3	13.5

At progression, patients on the control arm will be offered treatment with Zotiraciclib (TG02) in combination with continued treatment with TMZ. If an effective salvage regimen, this may impact the secondary OS endpoint, but will not affect the primary endpoint of the study. The maximum number is 80 patients.

Statistical Analysis Plan

We will use descriptive statistics to summarize the demographic and clinical characteristics of patients. We will tabulate adverse events by grade by dose level and overall. For the cohort expansion and phase II component, we will estimate the proportion of patients with response with 95% exact binomial confidence intervals, and use descriptive statistics to summarize response duration. We will estimate PFS/OS with the Kaplan-Meier product limit estimator. Log-rank test will be used to compare the PFS/OS between Zotiraciclib (TG02)+TMZ and TMZ.

Changes of symptom burden (i.e., MDASI-BT) through study time points will be assessed by paired t-tests and linear mixed model. In the mixed model, subject-specific random intercept will be used to account for within-subject correlation, and measurement time will be included as a covariate. A sample size of 40 patients has 80% power to detect an effect size of 0.454 between time points using a two-tailed test with an alpha of 0.05. The two-sample t-test and linear mixed model will be used to evaluate differences in symptom burden using the MDASI-BT between Zotiraciclib (TG02) plus TMZ and TMZ. Cox proportional hazard model will be used to evaluate the relationship between MDASI-BT and disease progression. Logistic regression will be used to evaluate the relationship between MDASI-BT and tolerance to treatment.

Treatment effects will be evaluated by advanced MRI imaging study. Perfusion and diffusion – based MRI parameters, including but not restricted to blood volume, blood flow mean and median Apparent Diffusion Coefficient (ADC) value will be analysed. Results will be summarized. The mean and median value at different time points will be tabulated. Changes in such parameters will be analysed for statistical significance and correlate with the disease status.

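### The response-evaluable definition requires a cycle at the MTD and a re-evaluation, so it does not fit the Phase II TMZ-alone arm (or a combination arm at MTD-1) and drops patients who stop unscanned

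*Combined protocol and SAP*

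**What the plan says.** Section 6.3.2 sets three conditions for response evaluability: measurable disease at baseline, at least one cycle at the MTD, and a re-evaluation. Patients must "have received at least one cycle of therapy at MTD and have had their disease re-evaluated". A note adds one exception: "Patients who exhibit objective disease progression prior to the end of cycle 1 will also be considered evaluable". Other definitions in the same section name Phase I where they mean it; this one does not.

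The MTD comes from the Phase I objective in section 1.1.1.1: "To determine the maximum tolerated dose (MTD) of Zotiraciclib (TG02) plus TMZ using both the dd and mn TMZ schedules". No MTD is defined for TMZ alone.

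Section 1.1.2 makes response a secondary objective: "To determine the objective response rate, PFS at 6 months (PFS6) and overall survival (OS) in the treatment arms". The analysis plan in section 10.2 says that, for the cohort expansion and Phase II, "we will estimate the proportion of patients with response with 95% exact binomial confidence intervals". It does not name the patients who form the denominator. Phase II has a control arm, described in section 10.2: "The TMZ alone arm will use the same dosing schedule as it is in the combination arm".

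Section 10.1 allows the Phase II dose to fall below the MTD: if the PFS4 difference is under 5%, the rule is to "select the lower dose, I.e., MTD-1, as the RP2D". Section 3.2.2 still derives the Phase II combination dose from the MTD.

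**The concern.** Section 6.3.2 is the only definition of response evaluability in the documents, and the analysis plan gives no other denominator for ORR. Applied as written in Phase II, it has two faults.

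- The MTD condition cannot be met by one arm, and possibly not by either.
- The re-evaluation condition selects on something that happens after randomisation. Patients who leave before their first scan cannot be responders, so removing them raises ORR. If the arms lose patients at different rates, it raises ORR unequally.

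At stake is a secondary endpoint that must be reported in each arm. If the definition is left alone, someone will have to choose a workable denominator after the data are in.

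**Working it through.** The documents state no response rate, power or sample size for ORR, so there is no figure to reproduce. The check sets the definition against each group and then illustrates the size.

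**Step 1. Can the group receive a cycle at the MTD?**

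| Group | Condition can be met? | Response estimate planned? |
|---|---|---|
| Phase I expansion at the MTD | Yes | Yes (10.2) |
| Phase I post-interim cohort, dose level 0 | No | No; only AE and PFS4 recorded (10.1) |
| Phase II TMZ alone | No | Yes (1.1.2, 10.2) |
| Phase II combination, run at the MTD | Yes | Yes |
| Phase II combination, run at MTD-1 | No | Yes |

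**Step 2. What the note does in a group that cannot meet the condition.** The note admits patients with objective progression before the end of cycle 1 and sets no dose condition. If k such patients exist, the evaluable set is those k patients, none a responder. ORR = 0/k = 0% for any k of 1 or more, however many other patients in the arm responded. If the combination arm is run at the MTD, this would favour it.

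**Step 3. Who leaves through the re-evaluation condition.** The first scheduled on-treatment MRI and response evaluation fall in week 4 of cycle 2, about 8 weeks in (3.5.2, 3.8). The off-study visit includes no MRI (3.8, 3.10.2).

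- Objective progression in cycle 1: kept by the note.
- Death or deterioration without a scan: section 6.3.4 counts failure to return for these reasons as progression. It does not say whether this is objective progression or a re-evaluation, and the note stops at the end of cycle 1. Status unclear.
- Toxicity stop or withdrawal before the week-8 MRI: nothing keeps these patients in.

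**Step 4. Size, on assumed inputs.** With x responders among n measurable patients and a fraction d unevaluated (all non-responders), ORR moves from x/n to x/(n(1 - d)). Assume n = 32 of 40, x = 4:

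- d = 0: 4/32 = 12.5% (exact 95% CI 3.5-29.0%)
- d = 0.10: 4/28.8 = 13.9%
- d = 0.20: 4/25.6 = 15.6%

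The shift is 1.4 to 3.1 percentage points.

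For a wider range, assume all 40 patients per arm are measurable, true ORR is 5-20% and loss is 5-30%. The shift then runs from 2/38 - 2/40 = 0.3 points to 8/28 - 8/40 = 8.6 points.

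For unequal loss, assume 4 responders of 40 in each arm, with 8 unevaluated in one and 2 in the other: 4/32 = 12.5% against 4/38 = 10.5%. A 2.0-point difference appears where there is none. It reverses sign if the losses are swapped.

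**The case against.** The strongest reply is that the intent is plain. The MTD phrase separates Phase I expansion patients from those at other dose levels, and in Phase II everyone would read it as the assigned regimen. ORR there is descriptive, and no stopping rule or sample size depends on it. The analysis plan names no denominator, so it does not expressly adopt section 6.3.2. Section 10.2.1 uses an intent-to-treat population when it compares symptoms in responders and non-responders, so other populations are in play. The numerical shift is small beside the confidence interval.

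Much of this stands. The phrase does useful work in Phase I and should stay there. The size is modest and its inputs are assumed. But intent is not text: the sentence is not confined to Phase I, and the silence in section 10.2 leaves the denominator open rather than correct. Section 6.3.6 does not close the gap either. It can leave a patient's best response unknown, which is not the same as a non-responder.

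A reader might infer three stronger things, which the documents do not support:

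- **The control denominator is zero.** The note admits cycle 1 progressors, so the literal set is those patients only.
- **All early failures are dropped.** Objective progression in cycle 1 is kept, and section 6.3.4 treats failure to return through death or deterioration as progression. The clear losses are toxicity stops and withdrawals.
- **A planned randomised comparison of ORR is lost.** Section 10.2 plans a proportion with an exact interval; the log-rank comparison covers PFS and OS only.

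**Conclusion.** The point holds as a defect in the definition. In Phase II the MTD condition cannot be applied to TMZ alone, nor to the combination arm if MTD-1 becomes the RP2D. Followed literally, it would return an ORR of 0% for such an arm regardless of the responses seen. The MTD-1 part is conditional on the PFS4 rule in section 10.1 and concerns Phase II only; no ORR is lost in the post-interim cohort.

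The re-evaluation condition is a second, smaller fault. It removes patients who stop for toxicity or withdraw unscanned, and leaves the status of unscanned deaths and deterioration unclear. On the assumed inputs the inflation is about 1.4 to 3.1 points, and 0.3 to 8.6 points over the wider range. Losses may differ by arm because only one arm starts on zotiraciclib, but the documents give no loss rates, so neither the direction nor the size of any imbalance can be stated.

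The primary PFS endpoint is unaffected. This should be corrected before Phase II data are analysed, but it does not threaten the main conclusion of the trial.

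**What to change.** 1. In section 6.3.2, keep the MTD condition for the Phase I expansion. For Phase II, replace it with *assigned protocol therapy*.
2. In section 10.2, state that Phase II ORR is estimated by assigned arm in all randomised patients with measurable disease at baseline, and that patients without a post-baseline assessment count as non-responders. Report the re-evaluated set as a sensitivity analysis.
3. State, for that sensitivity set, whether death or deterioration without a scan under section 6.3.4 counts as objective progression or as re-evaluation.
4. Reconcile sections 3.2.2 and 10.1 on where the Phase II combination dose comes from.

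The cost is wording only: no added patients, visits or scans. Reported ORR will be slightly lower than on the re-evaluated set.

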6.3.3 Disease Parameters

Measurable Disease: Bi-dimensionally measurable lesions with clearly defined margins by GD-DPTA enhanced MRI scan.

Evaluable Disease: Uni-dimensionally measurable lesions, masses with margins not clearly defined. Patients with only this kind of imaging will not be allowed to enter this study unless they have recently undergone surgery and have histologically proven recurrent disease.

Non-Evaluable Disease: Not Applicable for response evaluation.

Objective-Status, To Be Recorded at Each Evaluation: If there are too many measurable lesions to measure at each evaluation, choose the largest two to be followed before a patient is entered on study. The remaining lesions will be considered evaluable for the purpose of objective status determination. Unless progression is observed, objective status can only be determined when ALL measurable and evaluable sites and lesions are assessed.

6.3.4 Response Criteria

Response and progression will be evaluated in this study using the new proposed criteria Response Assessment in Neuro-Oncology Criteria (RANO) (see Appendix 15.5).[49]

Complete response: Requires all of the following:

- Complete disappearance of all enhancing measurable and non-measurable disease sustained for at least 4 weeks.
- No new lesions and stable or improved non-enhancing lesions (T2/FLAIR)
- Patient off steroids or on physiologic replacement only.
- Stable or improved clinically.

Partial response: Requires all of following:

- ≥ 50 % decrease compared to baseline (prior to treatment) in the sum of the products of perpendicular diameters of all measurable enhancing lesions sustained for at least 4 weeks;
- No new lesions and stable or improved non-enhancing lesions (T2/FLAIR).
- Patients off steroids or on physiologic replacement only.

- Stable or improved clinically.

Stable disease: Requires all of the following:

- Not complete response, partial response or progression.
- Stable non-enhancing lesions (T2/FLAIR).
- Patient on same or lower dose of steroids compared to baseline scan.

Progression: Requires any of the following:

- ≥ 25 % increase compared to baseline in the sum of the products of perpendicular diameters of enhancing lesions compared with the smallest measurement obtained either at baseline or best response with the patient on stable or increasing doses of steroids.
- Significant increase in T2/FLAIR non-enhancing lesions with the patient on stable or increasing doses of steroids (not caused by comorbid events e.g. Radiation therapy, demyelination, ischemic injury, infection, seizures, medication adverse events or changes in corticosteroid dose).
- Any new lesions.
- Failure to return for evaluation as a result of death or deteriorating condition or clear progression of non-measurable disease.

6.3.5 Patients will undergo response evaluations every 2 months.

- RANO criteria will be used to determine response and progression (includes CR, PR, SD and PD) **15.5**.
- Neurological exam.
- Performance status by Karnofsky Performance Status.

6.3.6 Evaluation of Best Overall Response

This will be calculated from the sequence of objective statuses. For patients with all disease sites assessed every evaluation period, the best response will be defined as the best objective status as measured according to Section **6.3.4**. If the response does not persist at the next regular scheduled MRI, the response will still be recorded based on the prior scan but will be designated as a non-sustained response. If the response is sustained, e. g. still present on the subsequent MRI, it will be recorded as a sustained response, lasting until the time of tumor progression. Best response is unknown if the patient does not qualify for a best response or increasing disease and if all objective status determinations before progression are unknown.

6.3.7 Duration of Response

Duration of overall response: The duration of overall response is measured from the time measurement criteria are met for CR or PR (whichever is first recorded) until the first date that recurrent or progressive disease is objectively documented (taking as reference for progressive disease the smallest measurements recorded since the treatment started).

The duration of overall CR is measured from the time measurement criteria are first met for CR until the first date that progressive disease is objectively documented.

Duration of stable disease: Stable disease is measured from the start of the treatment until the criteria for progression are met, taking as reference the smallest measurements recorded since the treatment started, including the baseline measurements.

6.3.8 Progression-Free Survival

PFS is defined as the duration of time from start of registration to time of progression or death, whichever occurs first.

6.3.9 Time to Death:

From date of registration to date of death due to any cause.

6.3.10 Neurological Exam:

Although not used for determining response, it is useful to evaluate improvement in the neurologic exam, (as compared to the baseline assessment), that should coincide with objective measurement of tumor size. The criteria are as follows:

- 0= No neurologic symptoms, fully active at home/work without assistance
- 1= Minor neurologic symptoms, fully active at home/work without assistance
- 2= Moderate neurologic symptoms, fully active at home/work but requires assistance
- 3= Moderate neurologic symptoms, less than fully active at home/work and requires assistance
- 4= Severe neurologic symptoms, totally inactive requiring complete assistance at home or institution, unable to work

